#### Success criteria:

A test product will be considered to have low photo-sensitisation potential if the proportion of subjects with a potential photo-sensitisation reaction are comparable for the test product and saline.

The hypothesis is that the study products will have low photo-sensitisation potential. Therefore, it is expected that the vast majority of responses will be negative. No formal statistical comparison between treatment groups shall be made.

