### 3 STUDY OBJECTIVES AND ENDPOINTS

**Table 3-1 Study Objectives and Endpoints**

Objectives	Endpoints
Primary	
To evaluate the cutaneous photo-sensitisation potential of three cosmetic facial skincare products compared to saline solution.	Proportion of subjects with a potential sensitisation reaction which is considered photo-initiated.
Secondary	
To evaluate the cutaneous photo-irritation potential of three cosmetic facial skincare products compared to saline solution.	Proportion of subjects with a photo-initiated reaction score of '+' or greater which is not considered a potential sensitisation reaction.
To evaluate the cutaneous sensitisation potential of three cosmetic facial skincare products compared to saline solution.	Proportion of subjects with a potential sensitisation reaction which is not considered photo-initiated.
To evaluate the cutaneous irritation potential of three cosmetic facial skincare products compared to saline solution.	Proportion of subjects with a non-photo-initiated reaction score of '+' or greater which is not considered a potential sensitisation reaction.
Safety	
To evaluate the general safety of three cosmetic facial skincare products	Frequency and severity of Adverse Events

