### 12.2.6 Primary Analysis(es)

The primary analysis will be based on the number of subjects with potential sensitisation reactions considered photo- initiated (i.e. potential photo-sensitisation reactions) and will be based on the safety population.

The assessment of potential sensitisation reactions in the challenge phase will be determined by the blinded dermatologist. Potential sensitisation reactions will be further classified as potential photo-sensitisation reactions using the following rules:

1. Positive reactions which occur at ONLY the UV-exposed site will be considered photo-initiated.
2. Positive reactions which occur at ONLY the non-UV-exposed site will not be considered photo-initiated.
3. Positive reactions which occur at BOTH the UV-exposed and non-UV-exposed sites will be considered photo-initiated if the maximum score at the UV-exposed site is more severe than the maximum score at the non-UV-exposed site. If the maximum score at the UV-exposed site is equal to or lower than the non-UV-exposed site, then it will not be considered photo-initiated.

The number and percentage of subjects with any potential sensitisation considered photo-initiated reactions versus those without any will be presented by treatment group. No formal statistical inference will be performed.

All potential sensitisation reactions considered photo-initiated will be listed.

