1.2 Study Objectives

The study objectives are as follows:

Objectives	Endpoints
Primary Objective	Primary Endpoint
To evaluate the cutaneous photo-Sensitization potential of three cosmetic facial skincare products compared to saline solution.	Proportion of subjects with a potential sensitization reaction which is considered photo-initiated.
Secondary Objectives	Secondary Endpoints
To evaluate the cutaneous photo-irritation potential of three cosmetic facial skincare products compared to saline solution.	Proportion of subjects with a photo-initiated reaction score of '+' or greater which not considered a potential sensitization reaction.
To evaluate the cutaneous sensitization potential of three cosmetic facial skincare products compared to saline solution.	Proportion of subjects with a potential sensitization reaction which is not considered photo-initiated.
To evaluate the cutaneous irritation potential of three cosmetic facial skincare products compared to saline solution.	Proportion of subjects with a non-photo-initiated reaction score of '+' or greater which is not considered a potential sensitization reaction.
Safety	
To evaluate the general safety of three cosmetic facial skincare products	Frequency and severity of Adverse Events

Success criteria:

A test product will be considered to have low photo-sensitization potential if the proportion of subjects with a potential photo-sensitization reaction are comparable for the test product and saline.

The hypothesis is that the study products will have low photo-sensitization potential. Therefore, it is expected that the vast majority of responses will be negative. No formal statistical comparison between product groups shall be made.

Developmental cosmetic moisturizers (a serum, lotion and cream)

212378

Statistical Reporting and Analysis plan Amendment 1, Text Final v1.0, 03 Sep 2019

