4.1.3 Analysis Populations

The analysis populations defined for this study are as follows:

Population	Definition / Criteria	Analyses Evaluated
Safety	The Safety population includes all randomized subjects who received at least one dose of any study product. This population will be based on the product sequence the subject received.	Primary endpoint, Secondary endpoints Safety
Randomized	All subjects randomized in induction phase regardless of whether they received study product. Any subject who receives a treatment randomization number will be considered to have been randomized.	Protocol deviations, disposition and medical history listings

NOTES :

- To be randomized into the challenge phase, a subject must have been already randomized in the induction phase. Therefore, the randomization status in challenge phase won't be considered to define the randomized population. Only the randomization in induction phase status will be used to define this population.
- Please refer to Attachment 1: List of Data Displays which details the population to be used for each of the displays being generated.

[Listing 16.2.3.1](#) will display all randomized subjects (induction phase) included and excluded from the safety population.

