If a subject discontinues prior to the last visit the subject will not be considered for endpoints of sensitization or photo-sensitization, the subject can still be included in endpoints of irritation or photo-irritation based on ICDRG scores.

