4.4.1 Primary Endpoint

4.4.1.1 Primary Endpoint Definition

The primary analysis will be based on safety population.

The primary analysis will be based on the number of subjects with potential sensitization reactions considered photo-initiated (i.e. potential photo-sensitization reactions).

Potential photo-sensitization reactions are defined as a positive reactions meeting both of the following requirements:

- sensitization reported as “yes” at final visit of challenge phase (sensitization box ticked “yes” on eCRF)
- the maximum score of the UV-exposed site (across all visits) during the challenge phase > maximum score of the non-UV exposed site (across all visits) during the challenge phase

The number and percentage of subjects with potential sensitization considered photo- initiated reactions will be presented by product group in [Table 14.2.2.1](#). No formal statistical inference will be performed.

All potential sensitization reactions considered photo-initiated will be listed ([Listing 16.2.6.3](#)) for the safety population.

A frequency table will be presented for potential sensitization reactions (Sensitization (Yes), non-sensitization (No) and Unable to determine) regardless of photo initiation status by product group in [Table 14.2.1.1](#).

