4.4.1.2 Statistical Hypothesis, Model, and Method of Analysis

No formal statistical inference is planned for primary endpoint.

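### A challenge reactor who leaves before Visit 23 drops out of the primary endpoint and is tabulated as irritation or photo-irritation, and 'low potential' is concluded without any measure of precision

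*Protocol*

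**What the plan says.** The primary objective in Protocol Table 3-1 is comparative: "To evaluate the cutaneous photo-sensitisation potential of three cosmetic facial skincare products compared to saline solution". The success criterion in Protocol section 3, repeated in SAP 1.2, is "A test product will be considered to have low photo-sensitisation potential if the proportion of subjects with a potential photo-sensitisation reaction are comparable" for test product and saline. Neither document gives a margin, a limit or a maximum count for 'comparable'.

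The analysis is openly descriptive. Protocol 12.2.6 plans: "The number and percentage of subjects with any potential sensitisation considered photo-initiated reactions versus those without any will be presented by treatment group". SAP 1.2 adds "No formal statistical comparison between product groups shall be made", SAP 4.4.1.2 states "No formal statistical inference is planned for primary endpoint", and SAP 4.4.1.3 lists no supportive analysis.

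On who is counted, SAP 4.4.1.1 says "The primary analysis will be based on safety population", and SAP 4.1.3 defines that set: "The Safety population includes all randomized subjects who received at least one dose of any study product". SAP 4.4 then adds: "If a subject discontinues prior to the last visit the subject will not be considered for endpoints of sensitization or photo-sensitization". The same sentence keeps such a subject available for the irritation and photo-irritation endpoints. SAP 4.4.3 and Protocol 12.2.9 include dropouts up to the point of discontinuation.

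The dermatologist classifies positive challenge reactions at the final visit (Protocol 5.8, 8.13 and 9.2.1). SAP 4.5.1 defines photo-irritation and irritation as positive reactions whose final-visit sensitisation entry is 'No', 'Unable to determine' or missing. The two are separated by whether the maximum score at the UV site exceeds that at the non-UV site.

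**The concern.** A missing verdict has two quite different sources. A subject who was positive only during induction is never classified by the dermatologist, so a missing entry is expected and irritation is a fair heading. A subject who was positive at challenge and left before Visit 23 has an unresolved reaction of exactly the kind the primary endpoint is meant to catch. SAP 4.5.1 does not separate the two. The second subject leaves the photo-sensitisation and sensitisation rows and appears in the irritation or photo-irritation row. With event counts expected near zero, one such subject can decide whether a product shows any potential photo-sensitisation at all.

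The precision issue adds to this. A zero, or one event against none, will probably be read as 'comparable', and no planned display shows how large a rate, or a difference from saline, remains compatible with the data.

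**Working it through.** **Plan's own figure.** Protocol 12.1 and SAP 1.4 give about 80 screened, at least 40 randomised and at least 25 evaluable. No error rate, power, event rate, margin or dropout rate is stated, so there is no calculation to reproduce. I use 25 and 40 as the ends of an assumed range; both are planned minimums. The 95% level is my choice.

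**1. Path of an unclassified challenge reactor**

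- Positive score ('+' or greater) at Visits 20 to 22, then discontinuation before Visit 23.
- SAP 4.4: not considered for sensitisation or photo-sensitisation.
- SAP 4.4.1.1: the primary endpoint needs a 'Yes' at the final visit. There is none.
- SAP 4.5.1: a missing verdict satisfies the first condition for photo-irritation and for irritation. The subject falls under photo-irritation if the UV-site maximum over both phases exceeds the non-UV maximum, and otherwise under irritation.

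*Worked case (assumed).* 25 subjects challenged; one reacts to a product with a higher UV-site score and leaves before Visit 23; nobody reacts to saline.

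- As written: 0/24 if the subject is removed altogether, upper limit 1 − 0.025^(1/24) = 14.2%; or 0/25 if kept as a non-event, upper limit 13.7%. Either way the primary row shows zero.
- Counting the reaction as potential photo-sensitisation: 1/25 = 4.0%, exact 95% limits 0.1% to 20.4%.

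**2. What zero events leaves open for one product**

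Exact two-sided 95% (Clopper-Pearson) upper limit for 0/n: 1 − 0.025^(1/n).

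| n | Upper limit |
|---|---|
| 25 | 13.7% |
| 30 | 11.6% |
| 35 | 10.0% |
| 40 | 8.8% |

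If the true rate were 5% (assumed), the chance of seeing no reaction would be 0.95^25 = 28% with 25 subjects and 0.95^40 = 13% with 40.

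**3. What it leaves open against saline**

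Every subject receives all three products and saline, so the comparison is paired. The 95% score (Tango) interval for product minus saline, when no subject is discordant, is ± z²/(n + z²) with z = 1.96 and z² = 3.8415.

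- n = 25: 3.8415/28.8415 = ±13.3 points.
- n = 40: 3.8415/43.8415 = ±8.8 points.

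With one subject positive on product only:

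- n = 25: +4.0 points (−9.9 to +19.5).
- n = 40: +2.5 points (−6.5 to +12.9).

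**The case against.** **The design is deliberately descriptive.** No power calculation, comparison or inference is claimed, and a reader given counts and denominators can work out an exact limit. That rules out calling the study underpowered or asking for a hypothesis test, and I do neither. But the success criterion still turns the percentages into a stated conclusion, and an interval is description rather than a test. Intervals will not define 'comparable'; they show what the judgement rests on.

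**The dermatologist may already have looked.** Protocol 4.1, section 8.5.4 and footnote b of the schedule have positive challenge reactions reviewed without fixing the time at the final visit, and Protocol 7.2 lets a re-contacted subject be asked back. The exposed window is only Visit 20 to Visit 23. This makes the problem rarer. It does not remove it, because SAP 4.4 drops the subject whatever was seen earlier and the endpoint definitions use the final-visit entry.

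**The reactions are not hidden.** This stands. Positive reactions go to Listing 16.2.6.2, irritation-type reactions to Listing 16.2.6.4 or 16.2.6.6, and challenge narratives to Listing 16.2.6.7. Table 14.2.1.1 also shows 'Unable to determine'. The fault is confined to the summary tables, on which the success criterion is likely to be judged.

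**The denominator.** A reader might infer that the SAP contradicts itself and that programmers would divide by different numbers. The documents do not support going that far. SAP 4.1.3 refers display populations to Attachment 1, which is not readable in the copy reviewed. The sentence in SAP 4.4 reads most naturally as removal from the endpoint. A denominator common to product and saline changes neither their ratio nor a zero count. Randomising 40 to secure 25 is a recruitment allowance, not a stated dropout rate. What remains is a clarification.

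**Conclusion.** The concern holds on two counts.

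1. As written, SAP 4.4 and 4.5.1 together move an unclassified challenge reactor out of the sensitisation endpoints and into irritation or photo-irritation. The direction is reassuring. The frequency is unknown and probably low, and no estimate can be taken from the documents. In the assumed case, one such subject is the difference between a primary result of zero and 1/25 (4.0%).
2. A conclusion of low photo-sensitisation potential would carry no measure of precision. With zero events, a true rate of up to 13.7% (n = 25) or 8.8% (n = 40) is not excluded, nor is a difference from saline of 13.3 or 8.8 points. These figures rest on a 95% level and on the planned minimums; more evaluable subjects would narrow them.

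The denominator wording is secondary. Nor should SAP section 5, which declares no change from the protocol, be read as plainly wrong: Protocol 12.2 leaves further detail to the analysis plan. But the exclusion in SAP 4.4 is not in the protocol, whose only dropout rule is section 12.2.9, so it should be recorded.

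**What to change.** Amend the SAP before unblinding, with no hypothesis test and no change to sample size.

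1. In Tables 14.2.1.1 and 14.2.2.1, show challenge-phase positive reactors with a missing verdict in a separate 'positive, unclassified' row. Do not report their challenge reaction as irritation or photo-irritation without that flag. Induction-only reactors stay as they are.
2. Add one sensitivity result that counts both missing and 'Unable to determine' challenge reactors as potential sensitisation, photo-initiated if the UV-site maximum exceeds the non-UV maximum in the challenge phase. Both states are unresolved and should be treated alike.
3. State the sensitisation denominator as challenged subjects who have the Visit 23 (72-hour) assessment, plus any subject with a positive challenge score. Give the Safety-population percentage as supportive. Requiring only one post-irradiation grading would be too loose: the protocol expects elicitation within 24 to 72 hours, so a subject seen only immediately after UV should not count as a non-event.
4. Report Clopper-Pearson 95% limits for each product and for saline, the paired discordant counts, and a 95% score interval for product minus saline. Label all of these descriptive, and place them beside any statement of 'comparable' or 'low potential'.
5. Reconcile the discontinuation sentence in SAP 4.4 with 4.4.3 and 4.5.1, and record the change in SAP section 5.

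The cost is a SAP amendment, a few table rows and columns, and a less favourable stated conclusion. The wording of the success criterion can stay.

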### 4 STUDY DESIGN

#### 4.1 Overall Design

This will be a single-center, randomised, evaluator (single) blind study in healthy adult subjects aged 18 to 65 years with no dermatological disorders to evaluate the cutaneous photo- irritation and photo- sensitisation potential of three cosmetic facial skincare products.

Approximately 80 healthy subjects will be screened to randomise at least 40 subjects to ensure at least 25 evaluable subjects complete the entire study.

There will be a total of 5 different test areas, located on the back of each subject, which will be used in this study across the screening, induction and challenge phases:

- 1 test area to determine the provisional MEDu in screening;

- 2 test areas for test products and reference product (saline solution) in the induction phase (1 series will be exposed to UV radiation, the other series will not);
- 2 test areas for test products and reference product (saline solution) in the challenge Phase (1 series will be exposed to UV radiation, the other series will not).

The 4 test areas in the induction and challenge phases will each undergo applications of an adhesive patch system. Within each patch system, there will be 6 circular cells, of which 4 will be used to host the study products and 2 will be left blank. In this study, each of the study products will be dispensed into 4 adjacent cells, in two duplicate series of patches, as per the randomisation schedule. Three cells will be used for the test products (serum, lotion and cream) and a fourth for the reference product (saline solution).

Subjects will be exposed to duplicate, repeated insult semi-occlusive patch applications of the test products and reference product (saline solution) over a three-week induction phase, and a further single application of the test products and reference product in a challenge phase.

During screening, subjects will sign an informed consent form and undergo a dermatological assessment to ensure they have no dermatoses on their dorsum (back) that might impact their safety or confound study outcomes, and to ensure a Fitzpatrick Phototype of II to IV.

Subjects will also undergo a colorimetry analysis of their skin type using the Individual Typology Angle (ITA°) which will be used to estimate MED.

Each subject's medical history and medication history will be reviewed, as well as inclusion and exclusion criteria after which, site staff will review [lifestyle considerations](#) and study visit requirements with eligible subjects.

Subjects who meet all specified inclusion and exclusion criteria and who agree to comply with all lifestyle guidelines and restrictions will be considered eligible for enrollment in this study.

Visit 1 (screening) may be combined with visit 2 (MED irradiation) if convenient for the subject and study site. However, visit 2 should occur no later than 7 days after visit 1.

At visit 2, eligible subjects will return to the study site and another dermatological assessment will be conducted for inclusion criterion 6 to ensure subjects remain eligible to continue in the study (if visits 1 and 2 are not combined). Any changes to concomitant medications will also be reviewed.

The MED of each subject will then be determined in a two-step procedure, see section [8.2.1 \(MED Irradiation\)](#) and [8.3.1 \(MED Determination\)](#) for details. This step is critical to ensure the selection of UV doses for the assessment of photo-sensitisation and photo-irritation are appropriate for each subject, enabling a robust UV-challenge of the patched sites without resulting in UV-induced erythema (sunburn).

In this study, one series of patched sites will be repeatedly exposed to 0.3 MED of UV radiation (290-400 nm) and a second controlled dose of 2.5 J/cm^2 UVA (340-400 nm) radiation per the study schedule.

### **Induction Phase (visits 4-18):**

During the induction phase (visits 4-18) there will be 6 patch application visits over 3 weeks. Each patch will contain a segregated sample of each of the test products and saline solution.

[figure not shown]
Duplicate series of each patch will be applied to the assigned test areas on Mondays and Wednesdays and shall remain in place for 24 ( $\pm$  4) hours.

**Monday:** Subjects will arrive at site and will be assigned to a random sequence of study products within the 4 cells of the patch system, per the randomisation schedule. The location of the test areas on the back of each subject will be determined by the investigator or designee based on the condition of the skin (e.g. free of moles, dermatoses etc.) and will not be randomised.

Subjects will be seated in standard room conditions (18-26°C) and instructed to avoid contact between the test area on their back and any other surface. The area for patch application will be designated between the scapula and waistline and away from the spinal mid-line. Baseline assessment of the test site area will then be performed by a trained, blinded evaluator per the grading scale in [Table 15-2 \(Appendix 2\)](#). This will act as the baseline reading for the induction phase.

Note, the second and third Monday visits (i.e. visits 9 and 14) will not include the randomisation step. However, these visits will include an assessment for signs and symptoms of irritation by a trained, blinded evaluator following UV irradiation the preceding Thursday (i.e. visits 7 and 12).

If a subject develops a score of 'Strong' (++) or greater at any point during the induction phase, the next patch will be applied to an adjacent naïve (i.e. previously untreated) site. If a score of 'Strong' (++) or greater occurs at the naïve site, no further patch applications will be made. Such reactive subjects will, however, progress to the rest and challenge phase unless, in the opinion of the Investigator, it would be unwise to do so.

**Wednesday:** Subjects will arrive at site after 24 ( $\pm 4$ ) hours after irradiation and will be seated for at least 15-30 minutes to the environment of standard room conditions (18-26°C) and instructed to avoid contact of the back area with any other surface. Test sites will be evaluated for signs of irritation by a trained, blinded evaluator as per grading scale [Table 15-2 \(Appendix 2\)](#).

Duplicate patches will then be applied to the back, please see Monday assessments for further details on patch application.

**Thursday:** Tuesday assessments to be repeated.

**Friday:** Subjects will arrive at site after 24 ( $\pm 4$ ) hours after irradiation and will be seated for at least 15-30 minutes to the environment of standard room conditions (18-26°C) and instructed to avoid contact of the back area with any other surface. Test sites will be evaluated for signs of irritation by a trained, blinded evaluator as per grading scale [Table 15-2 \(Appendix 2\)](#).

The process of patch applications, grading and UV-exposure shall be repeated for an additional two weeks.

